A serious adverse event (SAE) is any adverse event that results in one or more of the following outcomes:

- Death
- A life-threatening event
- Inpatient hospitalization or prolongation of existing hospitalization
- A persistent or significant disability/incapacity
- A congenital anomaly or birth defect
- An important medical event based upon appropriate medical judgment

AEs will be labeled according to severity, which is based on their impact on the patient. An AE will be termed “mild” if it does not have a major impact on the patient, “moderate” if it causes the patient some minor inconvenience, and “severe” if it causes a substantial disruption to the patient’s well-being. AEs will be categorized according to the likelihood that they are related to the study intervention. Specifically, they will be labeled definitely unrelated, definitely related, probably related, or possibly related to the study intervention.

Unanticipated events and deaths will be reported to the IRB within 10 days per institutional policy. Individual adverse events will be summarized and reported at continuing review without any subject level identifiable information. Any updates to study risks or benefits based on analysis of this study data or other new published research will be reported as a modification during continual review and may require updated consent. Determination of severity, SAE, and

unexpected event status will be decided by the PI. Adverse event documentation will be prepared and compiled by the research coordinator utilizing a standardized WUSTL reporting template.

Risks

Conventional burr hole craniotomy has a literature reported complication rate of 9%. The meta-analysis of middle meningeal artery embolizations demonstrated a composite complication rate of 2.1% in double arm studies²¹, especially significant as a greater proportion of embolization patients are maintained on anticoagulant medications. The largest individual study to date included 60 embolizations with no procedural related complications¹⁵. A meta-analysis including 15 studies with 193 procedures additionally reported no procedure-related complications²⁵.

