Expected risks to the subject due to the interventional procedure are minor pain and bruising at the catheter insertion site. About 5% of subjects may develop a hematoma, a collection of blood that may cause more bruising and pain than normal and may require intervention. Less likely, more serious risks of embolization procedures (<1%) include temporary neurologic deficits, blindness or cranial nerve palsy, or an anaphylactic reaction to the contrast dye.

There is a small risk (0.3%) of carotid artery dissection and/or stroke with permanent neurologic deficit from catheter injury or clot formation. Arterial perforation or brain hemorrhage is a life threatening but rare complication. Insertion site infection is exceedingly rare.

When procedures are performed through the radial artery, a combination of medications are used to prevent radial artery occlusion, which may be asymptomatic or may cause hand ischemia and the loss of the hand. Radial subjects receive a TR band at the conclusion of the procedure to maintain patent hemostasis. Radial artery occlusion is rare with these prevention measures. Femoral access subjects receive manual compression or a closure device and must be maintained on strict bedrest for 6 hours to prevent hematoma formation.

These risks are addressed in the consent form and are considered to be minimal or outweighed by the risk of multiple invasive surgical procedures or the risk to the patient by reaccumulation of the hematoma. Patients with known contraindications to angiography or comorbid conditions placing them at higher risk of procedural complications are excluded from study participation. The neurointerventional radiology department at BJH is a high volume center with experienced physicians and staff. Approximately 1200 outpatient diagnostic cerebral angiograms are performed each year and over 300 interventional procedures.

Study subjects will be followed for research purposes for 90 days and may continue long term follow up with their outpatient neurosurgeon. Study follow up visits occur at 30 days (± 7) post procedure, and 90(± 10) days post procedure. At each of these time points the subject will receive a head CT scan, neurologic assessment, and assessment of adverse events. Adherence to follow up visits will be tracked and reported.

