The original signed consent will be maintained in a binder in a locked office. Subjects will be assigned a unique study identification number at the time of consent. Subject level hard copies of documents will be maintained in subject binders in a locked office with no personal identifying information, only the subject ID number. This number will link to identifying protected health

information in a separate locked database accessible only to relevant research team members. Clinical study data will be entered into a secure database on RedCap under the study ID number to maintain patient data confidentiality. Only engaged research team members will have access to the RedCap database.

Safety and Analysis

Study progress and safety, including patient recruitment, retention/attrition, and AEs, will be reviewed quarterly (or more frequently if needed). An Annual Report will be compiled and will include a list and summary of AEs. In addition, the Annual Report will address (1) whether AE rates are consistent with pre-study assumptions; (2) reason for dropouts from the study; (3) whether all participants met entry criteria; (4) whether continuation of the study is justified on the basis that additional data are needed to accomplish the stated aims of the study; and (5) conditions whereby the study might be terminated prematurely. This report will be made available to the IRB at continuing review.

No external monitoring committee will be utilized due to the nature of the study. The study will be collectively monitored for safety and adverse events by the three interventional neuroradiology faculty. Any adverse events will be reviewed at both the Department of Neurosurgery and Department of Radiology QA/QI committee meeting. Additionally any adverse events will be reported to the HSR QA/QI review board at Washington University. Each faculty reports to the Conflicts of Interest Review Committee (CIRC) at Washington University, and currently none have any financial conflicts of interest relevant to this study and are unlikely to develop any during the study duration given there is no funding source for the project and no industry sponsored product being utilized. Should any FCOI arise, that research member will be removed from study participation in accordance with policies recommended by CIRC.

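### The mild and moderate adverse-event grades overlap, so identical events can be graded differently and, on a literal reading, a worse event can get the lower grade

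*Combined protocol and SAP*

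**What the plan says.** The Adverse Events section of the combined protocol and SAP states the basis of the scale: "AEs will be labeled according to severity, which is based on their impact on the patient". An event is "termed “mild” if it does not have a major impact on the patient, “moderate” if it causes the patient some minor inconvenience". It is severe "if it causes a substantial disruption to the patient’s well-being". The sentence that begins "Determination of severity, SAE, and" goes on to give these decisions to the PI. The research coordinator documents events on an institutional template.

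The same section defines seriousness separately, by a list of outcomes.

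The Risks section names the access-site events to be expected. These are minor pain and bruising and, in about 5% of subjects, a hematoma, described as a "collection of blood that may cause more bruising and pain than normal and may require intervention".

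The Safety and Analysis section provides for quarterly safety review and adds: "An Annual Report will be compiled and will include a list and summary of AEs". That report goes to the IRB at continuing review.

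**The concern.** A severity scale needs grades that exclude one another and rise in order. Here *mild* is defined by what the event is not (not major), and *moderate* by something small (a minor inconvenience). The small thing falls inside the negative definition. The two lower grades then do not separate events, and the space between a minor inconvenience and a substantial disruption, where one would expect *moderate* to sit, is not clearly assigned to it.

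At stake is whether a severity label means the same thing from one event to the next. Safety is a stated objective, the trial has no external monitoring committee, and for a non-serious event this label is the only intensity grade that the protocol describes. If the label depends on which clause the PI applies, a split of events into mild and moderate cannot be reproduced or interpreted.

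**Working it through.** No sample size, power or error rate is involved. The check is a logical one on the wording, plus one multiplication.

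**Inputs**
- The three definitions, the basis of grading and the PI's role: Adverse Events section.
- Hematoma in about 5% of subjects: Risks section.
- 200 patients planned for embolization: Participants section, repeated under Safety and Analysis.

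**Step 1: place the definitions on one scale of impact.** I treat *major impact* and *substantial disruption* as the same upper boundary, because the protocol does not distinguish them. *Moderate* can be read in two ways: as a ceiling (a minor inconvenience and no more) or as a threshold (at least a minor inconvenience).

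| Impact on the patient | Meets mild | Meets moderate, ceiling | Meets moderate, threshold | Meets severe |
|---|---|---|---|---|
| A. Less than a minor inconvenience | yes | no | no | no |
| B. Minor inconvenience | yes | yes | yes | no |
| C. Worse than B, but not major or substantial | yes | no | yes | no |
| D. Major or substantial | no | no | yes | yes |

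**Step 2: exclusivity.** Row B meets both mild and moderate on either reading, so the overlap does not depend on how *moderate* is read. On the threshold reading the overlap extends to row C (mild and moderate) and row D (moderate and severe).

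**Step 3: order.** On the ceiling reading, row C meets only mild, while row B, a lesser event, can be moderate. The worse event then has the lower grade.

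**Step 4: would a rule of taking the highest grade met be enough?** The protocol states no such rule. If it were added to the present definitions:
- ceiling reading: A mild, B moderate, C mild, D severe (still out of order);
- threshold reading: A mild, B moderate, C moderate, D severe (ordered).

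The rule therefore repairs the scale only if the wording also settles the threshold reading, which it does not now do.

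**Step 5: which expected events are exposed.** Expected access-site hematomas: 200 × 0.05 = 10. The Risks section says that such a hematoma may need intervention, but does not say how often or how much it affects the patient. How many of the 10 fall in row B or row C cannot be computed from the documents.

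**Step 6: what uses the grade.**
- The SAE definition uses outcomes.
- Reporting to the IRB within 10 days applies to unanticipated events and deaths.
- The safety comparison in the Statistical Analysis section uses the rate of procedure-related complications.
- The first stopping criterion speaks of adverse effects that put safety in doubt, and names no grade.
- Review at the two departments' quality meetings and by the university's quality board covers any adverse event.

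None of these depends on the grade.

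**The case against.** The strongest reply is that the inversion needs an asymmetric reading: *mild* as a wide range, *moderate* as a narrow ceiling. A worse event also causes at least a minor inconvenience, so *moderate* can be read as a threshold. With the highest grade assigned, the scale is then ordered. This stands as far as it goes. The inversion is possible, not settled. But the threshold reading and the highest-grade rule both have to be supplied by the reader, and without them the overlap remains on either reading.

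Second, need for intervention is not a grading criterion. The PI may judge a treated hematoma to be a substantial disruption and grade it severe. That is correct, and it means that no fixed grade can be assigned to such an event. It also shows how widely the grade can vary on the same facts.

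Third, a low grade hides nothing. An event graded mild can still be an SAE. Three faculty members monitor adverse events together, and every event goes to quality review whatever its grade. This also stands, and it limits the consequence to the severity label.

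Finally, the institutional template might define the grades better. It is not part of the documents, and nothing in the protocol says that it replaces the definitions given there.

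**Conclusion.** The definitions of mild and moderate are not mutually exclusive, and nothing else in the documents resolves the overlap. That follows from the wording alone. On a literal reading, an event between a minor inconvenience and a substantial disruption can also be graded below a lesser one. The result is inconsistent grading at the PI's discretion, and an unreliable severity breakdown wherever one is reported. The access-site hematomas, about 10 in 200 patients if the protocol's 5% holds, are the clearest expected example.

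Three stronger readings are tempting, and the documents do not support them:
- A reader might infer that the two lower grades are definitely reversed. That holds only if *moderate* is a ceiling.
- A reader might infer that up to 10 hematomas will be misgraded. The 10 is an expected count of hematomas. No proportion needing intervention is given, so no number of affected grades follows.
- A reader might infer that the grade drives the stopping decision or the safety endpoint. Neither names it, and the Annual Report is not said to summarize events by grade.

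This is a real but bounded fault in severity reporting. Efficacy results, SAE capture and the complication-rate comparison are untouched.

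**What to change.** Replace the three definitions with exclusive, ordered ones that keep the scale's own basis, impact on the patient. For example:
- mild: no more than a minor inconvenience;
- moderate: more than a minor inconvenience, but short of a substantial disruption;
- severe: a substantial disruption to well-being.

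State that the highest grade met is assigned, and regrade any events already logged. Carry the same wording into the reporting template if it contains definitions. Need for intervention does not have to be added to repair the overlap; whether to use it as a criterion is a separate choice.

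The cost is one paragraph in the protocol and a little regrading work. Some events may move from mild to moderate and others from moderate to mild, so severity counts reported before and after the change should not be compared until the regrading is done.
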